# STUDY PROTOCOL

## 1. PROJECT TITLE

A Clinical Trial of Mobile Telephone based Assessment and Intervention for Persons with Bipolar Disorder or Schizophrenia

## 4. ESTIMATED DURATION OF THE STUDY

5 Years

## 5. LAY LANGUAGE SUMMARY OR SYNOPSIS (no more than one paragraph)

The purpose of this study is to evaluate the effectiveness of a mobile real-time cognitive behavioral intervention for serious mental illness (SMI) and to identify the facilitators, barriers, and costs of implementation. We would like to determine whether the addition of a mobile phone monitoring software program to a brief behavioral intervention for bipolar disorder or schizophrenia improves symptoms arising from the disorders. In this study we will be assessing the feasibility, acceptability and short term effect of the mobile phone enhanced intervention for bipolar disorder and schizophrenia. In addition, we will gather data from self-report measures and neuroscience-based tests from participants to inform future efforts in designing interventions aimed at diminishing risk of suicide in this population.

## 6. SPECIFIC AIMS

The goal of the study is to evaluate the effectiveness of a mobile real-time cognitive behavioral intervention for serious mental illness (SMI) and to identify the facilitators, barriers, and costs of implementation.

Our intervention called CBT2go builds on our extensive preliminary work using mobile devices, integrating ecological momentary assessment (EMA) with CBT content in BD and SZ. EMA is an ambulatory data collection technique that allows the *in vivo* assessment of moods, symptoms, medication adherence, social interactions and other daily activities. CBT2go delivers personalized thought challenging and behavioral coping interventions based on EMA's real-time reports. CBT2go is a 12-week intervention that involves a single in-person session followed by personalized yet automated responding on a mobile device, targeting affective and psychotic symptoms, medication adherence, socialization, and relapse prevention.

We are proposing a 6-month randomized controlled trial, with 255 participants recruited from the San Diego County public mental health system who have no current access to CBT. Participants will be stratified by diagnosis (BD or SZ), and will be randomized to receive CBT2go, EMA only, or Standard Care. This design will evaluate the added benefit of CBT components over EMA only (device contact, medication reminders, symptom monitoring), as well as the benefits of these components relative to Standard Care. Individuals will be assessed at baseline, mid-point (6 weeks), post-treatment (12 weeks) and 3-month follow up (24 weeks). Our primary and secondary outcomes will be measured with lab-based clinical ratings as well as EMA-based outcomes. We will also identify moderators (diagnostic group, cognitive ability) and mechanisms of change with respect to the elements of CBT

theory (changes in insight and dysfunctional attitudes). To inform pathways to implementation, we will evaluate the costs, barriers and facilitators to adopting CBT2go, with innovative methods from our implementation research. In addition, we would like to perform multiple blood draws on a subset of BD participants to determine whether variability in inflammatory markers, mood and cognitive performance predicts future suicide ideation in this population.

**Aim 1 (Effectiveness):** To determine the impact of CBT2go on primary and secondary outcomes.

**Hypotheses 1 (Primary Outcome):** Compared to EMA and Standard Care, the CBT2go intervention will be associated with greater improvement in global psychopathology (as measured by BPRS Total Score).

**Hypotheses 2 (Secondary Outcomes):** Compared to EMA and Standard Care, the CBT2go intervention will be associated with greater improvement in EMA and standard lab-based measures of medication adherence, social functioning, and hospitalization and emergency service utilization.

**Aim 2 (Moderators and Mediators):** To determine the impact of moderators and mechanisms on outcomes.

**Hypothesis 3 (Cognitive Impairment and Diagnosis):** Neurocognitive ability will account for more variation in device compliance and treatment response than diagnostic group.

**Hypothesis 4 (Awareness and Attitudes):** Improvement in illness awareness and reduction in dysfunctional beliefs will mediate incremental benefit of CBT2go over comparison conditions.

**Exploratory Aim 3:** Explore a predictive model for suicidal ideation in bipolar disorder that includes direct and indirect effects of cognitive performance, inflammatory cytokine levels, and trajectories of negative affect.

**Supplement Aim 1: To evaluate the association between baseline trait and dynamic impulsivity/social threat with lifetime suicide risk and intensity of and intra-individual variability in suicidal ideation**

**Hypothesis 1:** Impaired performance on impulsivity and social threat measures will be associated with higher lifetime rates of suicide attempts, and more severe and more variable suicidal ideation over 24 weeks

**Exploratory:** We will examine these effects by diagnostic group and treatment group assignment

**Supplement Aim 2: Test the accuracy of prediction models with intensive longitudinal data in the two-week window of time before increases in suicidal ideation**

**Hypothesis 2:** Accuracy of our prediction method will be greater than AUC=0.85 in predicting increases and will be greater than that associated with baseline suicide risk

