**Intervention Procedures (CBT2go, EMA-Only, and Standard Care Conditions):**

**Device:** As in previous trials, we will use the touch-screen Samsung Fascinate, a 4G Android OS smartphone. These devices will have a data plan (and can receive incoming calls). We will provide this device to participants. Participants will be informed that if they lose or damage the device they will not be held responsible.

**Device Training:** Device training covers how to operate the device, the meaning of all questions and response choices, and procedures for carrying the device and responding to alarms. Participants will also be trained in how to access and use crisis lines. This session will be individually-tailored to the learning needs of each participant, until participants can complete a trial run and feels

comfortable with the device. The Project Therapist or PI will be available to answer questions every day.

**EMA Protocol:** Interactions are triggered by a text message sent via an SMS gateway (with a “shortcode” referenced to our study), which automatically opens the browser wrapper that displays questions and alerts participants with vibration or ringtone. The timing can be adjusted to accommodate each participant’s preferences (e.g., sleep and wake schedules) and alarms can be silenced for 30-minute intervals (e.g., during driving). All data entries will be time stamped and responses recorded in real time. Data are accessible at all times only to study staff on a password protected server. If participants stop responding before the end of the questions, the data are still recorded; participants cannot “backfill” surveys as they expire in 15 minutes of the terminal alarm. Labeled on the back of the device is the investigator contact information and crisis line information. Participants will be instructed to answer the surveys and then return with the device at Week 12.

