**EMA Questions:** Participants will respond to surveys three times per day for 12 weeks. The frequency (3 times per day, morning, mid-day, evening) and timing (random initiation at approximately 2 hour intervals) of EMA surveys are based on preliminary data described above. In each of morning, mid-day, and evening surveys, participants will be prompted to answer multiple-choice questions (i.e., they do NOT type in answers) asking: What are you doing? (e.g., working, non-physical leisure), Who are you with? (e.g., alone, with family), Where are you? (e.g., at home, at work), and 7-point Likert scales are used to rate mood and symptoms (e.g., Are you sad? “Not at all” to “Extremely” or Have you been bothered by voices? “No voices” to “Extremely”). They also report whether or not they have taken prescribed medications and the number of social interactions since the last signal. The format of these questions is identical between EMA-only and CBT2go.

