**CBT2go Condition. Automated Interventions:** In CBT2go, responses to surveys branch to intervention content with a focus on challenging dysfunctional beliefs. For instance, if a patient reports that s/he missed a medication dose because "medication is not helpful", a personalized message is presented that challenges accuracy of this belief and the consistency of the non-adherence behavior with previously established values ("*You said taking your medication has helped improve your sleep before and that you valued getting a good night's rest*"). Similarly, if a patient reports that auditory hallucinations cannot be controlled, personalized contradictory evidence to challenge the belief is presented ("*But talking with your mother has quieted your voices in the past.*"). Moreover, for illness triggers that have been identified, "if-then" statements provide strategies that were successful in the past ("*when you've felt lonely, it helped to take the dog for a walk*"). Patients are also reinforced by the mobile device for endorsing freedom from symptoms for when describing

positive states (e.g., “What is helping?”).

**Technical and Follow-Up Support (EMA-only and CBT2go):** Participants will be contacted by phone in the first week after receiving the device and thereafter every two weeks to briefly check in (target 10 minutes) about their experience with the device. Although this contact is minimal, substantial research suggests human oversight of technology-based interventions is associated with greater adherence and efficacy. In case of crises (see Human Subjects for safety precautions) or difficulties with the device, participants can notify Project Manager or PI through the device, and a log will be kept of all ad-hoc contacts. Participants can obtain a new device at no cost in case of malfunction or loss.

**Standard Care Condition:** Participants will not be provided with a device or receive any study interventions, but will receive all study assessments and continue to participate in all ongoing treatments in the community. As seen Human Subjects, participants in crisis will be evaluated and referred to services.

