additional back-up from the Clinical Response Team. Given that all participants must be currently participating in stable outpatient care, the need for immediate emergency services will be unlikely. Nevertheless, based on our experience conducting clinical research in serious mental illness, we have developed the above plan to intervene appropriately should such a need arise.

**Experimental Conditions (Week 1 through Week 12):** Participants in the CBT2go and EMA-only conditions will be provided a smart-phone device with which to answer questions about their mood, activities and contexts. After baseline interview (and in-person session if in the CBT2go condition), participants will be asked to respond to questionnaires on the device until Week 12. Participants in the Standard Care condition will not be provided a device. We have taken several steps to ensure participant safety during the periods of no in-person contact. All participants will be provided with staff contact information and emergency resources in a printed manual, and they will be instructed that they may call the PI or project manager at any time in case of questions or emergencies. Participants must provide release of information for our staff to contact treating psychiatrists or other appropriate healthcare provider, so any emergent crises will be relayed to that participant's provider. In the CBT2go and EMA-only condition, responses at the severe spectrum of the mood or voices scales are accompanied with a screen that instructs participants to contact both emergency services (911 can be directly accessed via the device) AND project staff, if in crisis. We will monitor these protocols during the course of the study and will make adjustments to inclusion/exclusion criteria in case of adverse events.

**Data and Safety Monitoring Board:** The study will be reviewed annually through the UCSD DSMB. The board consists of non-UCSD faculty in psychiatry, community members, and bioethicists.

**Blood Draw:** Blood samples will be drawn only by research staff trained and certified in phlebotomy. Staff will take care to assure the participant is comfortable and participants will be provided with the necessary medical equipment (e.g. band-aids) to care for any irritation at the site of the blood draw.

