**Power Analysis:** The lack of prior RCTs of mobile interventions in BD or SZ makes it challenging to determine the effect size with which to power the study. The underlying assumption of our RCT is that effect sizes will be comparable to that seen in in-person CBT; Accordingly, we conservatively powered the study based results of recent meta-analyses of CBT in SZ and BD in a total of 46 RCTs, which revealed a median effect size of 0.4 (small to moderate) in favor of CBT with active comparators. Sample size estimates were based on the Hedeker, et al. method for various covariance structures for mixed effects models. For the proposed study, we assumed an autoregressive covariance structure, with conservative correlation between sequential assessments set at 0.5. Using this methodology, assuming an alpha level of 0.05, we have a minimum 80% power to detect a medium effect size with 20% attrition at 12 weeks (based on pilot data) when there are 85 subjects per each condition for a total of 255 subjects.

**Hypothesis 2 (Secondary Outcomes):** Compared to EMA-only and Standard Care, the CBT2go intervention will be associated with greater improvement in EMA and standard lab-based measures of medication adherence, social functioning, and hospitalization and emergency service utilization. **Dependent Variables:** EMA-outcomes; Medication adherence Composite; SFS Score; PSR Toolkit Composite and Hospitalizations/ER visits. **Independent Variables:** Condition and Time (0,6,12,24 Weeks).

**Statistical Analysis:** As above, this hypothesis will be tested using GAMMs. Condition will be entered into the model as a fixed-effect predictor along with time on study and their interaction, and we will test for all pairwise differences (e.g., CBT2go vs. Standard Care) with Westfall-Young adjusted p values. EMA outcomes (which include up to 252 observations per person) will be assessed with Hierarchical GLM analyses with a multinomial sampling model with a logit link functioning, with time (days in study) as a predictor and Condition (CBT2go vs. EMA-only) as a predictor of intercept and growth parameters of the model.

**Power Analysis:** Our secondary outcomes have the same assumptions as those in Hypothesis 1 and thus are independently powered to detect a medium effect size for each measure. The power to detect differences by condition with EMA analyses should be equal or greater by virtue of number of observations.

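### Hypothesis 2 claims an EMA comparison with Standard Care that the design cannot supply, and the EMA model that is planned has no baseline covariate and no named deciding test

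*Protocol*

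**What the plan says.** Protocol section 6 states Hypothesis 2 with two comparators and two kinds of measure in one sentence: "Compared to EMA and Standard Care, the CBT2go intervention will be associated with greater improvement in EMA and standard lab-based measures of medication adherence". The SAP restates it without limiting the EMA part: "Compared to EMA-only and Standard Care, the CBT2go intervention will be associated with greater improvement in EMA and standard lab-based measures of medication adherence". It then lists EMA outcomes among the dependent variables, under Condition and Time at weeks 0, 6, 12 and 24.

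The protocol's intervention procedures say of Standard Care: "Participants will not be provided with a device or receive any study interventions". That arm nevertheless "will receive all study assessments and continue to participate in all ongoing treatments in the community".

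For the device arms, section 15 says: "After baseline interview (and in-person session if in the CBT2go condition), participants will be asked to respond to questionnaires on the device until Week 12". The EMA sections add "Participants will respond to surveys three times per day for 12 weeks" and "Participants will be instructed to answer the surveys and then return with the device at Week 12".

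The SAP gives EMA outcomes a separate hierarchical model, with a multinomial logit link and up to 252 observations per person, "with time (days in study) as a predictor and Condition (CBT2go vs. EMA-only) as a predictor of intercept and growth parameters of the model". It names no other predictor for that model.

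**The concern.** There are two separate problems.

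First, the hypothesis and the design do not match. A contrast needs data on both sides, and Standard Care contributes no EMA. The listed week 0 and week 24 points cannot apply to EMA in any arm. If the hypothesis stands as worded, a reader of the results cannot tell which parts of it were tested.

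Second, greater improvement is not tied to a parameter. Surveys begin after the in-person session, and in CBT2go the survey responses branch to intervention content. No pre-treatment EMA period is described, so the model's intercept is already a post-treatment level. Improvement is naturally read as change over time, that is, growth. On that reading, a benefit present from the first days would appear as a difference in starting level and could be mistaken for chance imbalance. A model that lists only time and Condition offers no baseline covariate to help separate the two.

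**Working it through.** **1. The EMA window.** Inputs are three surveys a day for 12 weeks (protocol, EMA Questions) and a maximum of 252 observations (SAP, Hypothesis 2). 3 x 7 x 12 = 252, which reproduces the SAP figure exactly. A 24-week window would give 3 x 7 x 24 = 504. The SAP's own count therefore implies EMA for 12 weeks and none afterwards.

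**2. What exists in each arm.**

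| Data | CBT2go | EMA-only | Standard Care |
|---|---|---|---|
| EMA before treatment | none described | none described | no device |
| EMA, weeks 1-12 | yes | yes | no device |
| EMA, weeks 13-24 | none | none | no device |
| Lab-based, weeks 0, 6, 12, 24 | yes | yes | yes |

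Of the two EMA contrasts that Hypothesis 2 names, one exists. Both lab-based contrasts exist.

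**3. What each parameter would pick up.** The documents give no onset time or EMA effect size, so this step rests on assumptions. Take a true arm difference of 0.4 scale units, reached linearly by day r and then held: D(t) = 0.4 x min(t/r, 1), for t = 1 to 84. Fit a straight line by least squares.

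- Slope: b = sum[(t - 42.5) D(t)] / sum[(t - 42.5)^2]. The denominator is 84 x (84^2 - 1)/12 = 49,385. Growth over the period is 84b.
- Mean level: m = 0.4 x [1 - (r - 1)/168].
- Intercept at day 0: a = m - 42.5b.

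Example, r = 14: m = 0.4 x (1 - 13/168) = 0.3690. The fit gives 84b = 0.1658, so b = 0.001974 and a = 0.3690 - 42.5 x 0.001974 = 0.285. Growth recovers 0.1658/0.4 = 41%, and the mean level recovers 0.3690/0.4 = 92%.

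| Full benefit by day r | Growth over 84 days (share of 0.4) | Intercept, day 0 | Mean, days 1-84 (share of 0.4) |
|---|---|---|---|
| 1 | 0.00 (0%) | 0.40 | 0.40 (100%) |
| 7 | 0.08 (20%) | 0.34 | 0.39 (96%) |
| 14 | 0.17 (41%) | 0.29 | 0.37 (92%) |
| 28 | 0.30 (75%) | 0.18 | 0.34 (84%) |
| 56 | 0.44 (110%) | 0.05 | 0.27 (67%) |
| 84 | 0.40 (100%) | 0.00 | 0.20 (51%) |

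The 110% arises because a straight line is fitted to a bent curve.

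**4. A second assumed shape.** With D(t) = 1 - 2^(-t/h), fitted at mid-day points over the 84 days, growth recovers 0% of an immediate effect, 28% at a half-life of 3 days and 55% at 7 days. The intercept recovers 100%, 81% and 61%. The pattern is the same.

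**The case against.** The strongest reply is that the specific sentence in the SAP governs. The EMA model uses days in study and restricts Condition to the two device arms, which excludes Standard Care and the four-visit time grid. The 0, 6, 12 and 24 listing is one summary line for all Hypothesis 2 outcomes. This stands: a reader might infer that the sponsor plans a test on data that do not exist, and the documents do not support that.

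A reader might also infer that the planned model misses early benefit. It does not, because Condition predicts the intercept as well as growth. Under randomisation an early difference in level is a valid treatment contrast. The loss in the growth column occurs only if growth alone decides, which the SAP neither says nor rules out.

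Nor does the lack of a pre-treatment EMA period make the randomised comparison invalid. What is lost is baseline precision and within-person change from an untreated level.

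Finally, the mean level is not clearly the better choice. For a benefit that builds over most of a 12-week intervention it falls to 67% or 51%, where growth recovers all of it. The calculation is also a noise-free straight-line fit on a continuous scale, whereas the SAP specifies a multinomial logit model and the EMA outcomes include a yes/no adherence item and counts of interactions. It shows direction and rough size, not power or bias in the planned analysis.

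**Conclusion.** The point holds in limited form. Two statements follow from the documents without any assumption: the EMA contrast with Standard Care, and the week 0 and week 24 time points for EMA, cannot be delivered by this design. It also follows that the EMA model, as written, has no baseline covariate and no stated rule linking intercept and growth to the claim of improvement.

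The size of the second problem depends on onset, which is assumed. Growth alone recovers 0 to 41% of a benefit complete within two weeks and 75% or more of one that takes four weeks or longer. The mean level runs the other way, from 100% down to 51%. Neither is best throughout.

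This concerns one family of secondary outcomes. The primary BPRS comparison and the lab-based comparisons with Standard Care are unaffected.

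**What to change.** 1. Reword Hypothesis 2 in both documents so that the EMA part is CBT2go versus EMA-only over weeks 1-12. Take EMA outcomes out of the 0, 6, 12 and 24 week line. Rest the Standard Care comparison on the lab-based measures.
2. Add to each EMA model the matching baseline measure already collected: the BPRS depression, mania or hallucination item for symptoms, the self-report adherence scale for medication, and the SFS for socialisation. This should gain precision and partly makes up for the missing EMA baseline.
3. Specify one deciding test that counts both early and late benefit, and do not judge the EMA effect on growth alone. A joint test of the intercept and growth terms does not depend on where time is centred, but it has no direction, so the plan must say what pattern counts as benefit. The difference in mean model-based level over days 1-84 gives one directional estimate, but it dilutes a slowly building benefit (67% recovered for onset by day 56, 51% by day 84). Either is defensible; state the choice and the trade-off.

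The cost is wording and model specification only, with no new data. The hypothesis loses a claim that it could not support. The SAP's cover letter describes the trial as completed, so if the EMA results have already been seen, the deciding test should be reported as chosen afterwards.

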## **8. PROGRESS REPORT**

We are in Year 3 of the 4 year NIMH Award and have recruited and randomized 143 people out of the targeted 255 participants. We have submitted all required data to our sponsor, the NIMH, and have met or exceeded all recruitment targets to date. There are approximately 112 more people to randomize. We have had excellent retention in the trial (96%) and we have had no complaints from participants. We have not reported any data from this trial as the randomization is not locked. The study is listed on Clinical Trials.gov and its actively recruiting.

There have been no Adverse Events in our research study. We have participated in two annual DSMB meetings, the most recent of which was in January 2015. The board voted to approve the study and raised no concerns that required changing any of the protocols, commending the study on its success in recruiting and retention of participants.

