**PSR Toolkit (Secondary Outcome):** The PSR Toolkit is used to collect objective information on employment, residential situation, and hospitalizations/ER visits. The measure requires no subject testing burden, because research staff complete the PSR Toolkit (with participant release of information) by obtaining medical records, employment status records, visiting residential settings to determine level of services (With release of information for each of these obtained).

**Columbia-Suicide Severity Rating Scale (Secondary Outcome):** The C-SSRS is a semi-structured interview used to measure both behavior and ideation of suicidality. It is evidence-based, and well-supported.

**Cognitive ability (Moderator, Baseline only):** Cognitive ability will be measured with the MATRICES Consensus Cognitive Battery (MCCB) developed through systematic selection and psychometric evaluation of the tests involved.

**5 Choice-Continuous Performance Task (5C-CPT):** The 5C-CPT is a computer task of sustained attention and response inhibition that was developed based on a rodent paradigm.

**Suicide Related Phenotypes:** As noted above, we already administer the Columbia Suicide Severity Rating Scale (CSSRS) Lifetime (baseline) and Interval assessments (follow-ups). The CSSRS is part of the PhenX Suicide Specialty Collection. The CSSRS provides indices related to active ideation and behavior, but we lack more subtle measures of ideation or protective factors. The SSI will be the primary dependent variable for Supplement Aims 1 and 2.

- **Scale for Suicidal Ideation (Baseline, 6, 12, 24):** The Scale for Suicide Ideation (SSI) is a 21-item, interviewer-administered scale assessing intensity attitudes, behaviors, and plans to commit suicide on the day of the interview. This scale will provide additional continuous information about the intensity of current ideation beyond that already collected in the CSSRS. We will omit the final 2 questions that concern historical attempts, because that information is already gathered by the CSSRS. The SSI is a recommended measure from the Suicide Specialty Collection of the PhenX toolkit.

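### Supplement Aim 2 claims prediction in the two weeks before ideation increases, but the SSI dates an increase only to a 6- or 12-week gap, and pre-visit EMA exists only for weeks 6 and 12 in the two device arms.

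*Protocol*

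**What the plan says.** Protocol section 6 sets Supplement Aim 2 as testing prediction models built on intensive longitudinal data "in the two-week window of time before increases in suicidal ideation". Its Hypothesis 2 is that accuracy "will be greater than AUC=0.85 in predicting increases and will be greater than that associated with baseline suicide risk".

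The measurement plan is in Protocol section 9:

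- **Outcome.** "The SSI will be the primary dependent variable for Supplement Aims 1 and 2". The SSI covers attitudes, behaviors and "plans to commit suicide on the day of the interview". Table 1 schedules it at baseline and weeks 6, 12 and 24.
- **EMA, device arms.** "Participants will respond to surveys three times per day for 12 weeks", and "Participants will be instructed to answer the surveys and then return with the device at Week 12".
- **EMA, Standard Care.** "Participants will not be provided with a device or receive any study interventions".
- **EMA content.** The listed items cover mood and symptoms (depression, voices, mania), medication, social contact, activity, company and location. No suicidal ideation item is listed.
- **Other ideation data.** The C-SSRS is given in lifetime form at baseline and interval form at follow-ups. Thirty BD participants in EMA-only are also to complete it at home visits on about days 7 and 14.

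Neither document defines an increase, says how its onset is dated, or limits the aim to arms and visits that have EMA. The SAP covers Hypotheses 1 to 4 and contains no analysis for either Supplement Aim.

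**The concern.** The aim asserts an order in time: EMA first, then the rise in ideation. The named outcome shows only that the score on one interview day is higher than on another interview day 6 or 12 weeks before. The rise may have begun at any point in between, so EMA from the 14 days before the visit may precede it, straddle it or follow it.

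The stake is what a good AUC would mean. Protocol section 7 places this work under near-term suicide risk. A model that recognizes ideation already present could meet the accuracy target and be reported as advance warning. The two claims differ, and later work might rely on the stronger one. The primary BPRS comparison is not affected.

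**Working it through.** **1. EMA coverage.** The SAP gives up to 252 EMA observations per person. Three per day × 7 days × 12 weeks = 252, which matches exactly and confirms that EMA covers weeks 0 to 12 only. A 14-day window holds up to 3 × 14 = 42 prompts.

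**2. Which SSI visits have two weeks of EMA before them.** I take intensive longitudinal data to mean EMA; the Protocol does not say so outright.

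| Arm | Week 6 | Week 12 | Week 24 |
|---|---|---|---|
| CBT2go | yes | yes | no |
| EMA-only | yes | yes | no |
| Standard Care | no | no | no |

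Four of 9 cells are covered. With 85 per arm (SAP, Hypothesis 1 power analysis), that is 170 × 2 = 340 of 255 × 3 = 765 planned follow-up visits, or 44.4%. Applying the SAP's 20% attrition at week 12 to both visits leaves 340 × 0.8 = 272.

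The SSI was added when 143 people were already randomized; section 8 says "There are approximately 112 more people to randomize". If only those 112 receive it (assumption), 112 × 2/3 ≈ 75 are in device arms, giving 75 × 2 = 150 visits.

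**3. How well an increase can be dated.** The gaps between SSI visits are 6, 6 and 12 weeks. Assume one onset, uniform over a 6-week gap, that persists to the visit:

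- The share of onsets in the last two weeks is 2/6 = 33%.
- Let u be the weeks from onset to visit. The 14-day pre-visit window overlaps the true 14-day pre-onset window by max(0, 2 − u)/2. Its mean is (1/6) × ∫₀² (2 − u)/2 du = 1/6 = 16.7%.

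These are illustrations. Nothing in the documents fixes the distribution of onsets.

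**4. Precision of the AUC.** The documents give no sample size, event rate or precision for the 0.85 target. I used the Hanley–McNeil standard error with n₁ visits showing an increase and n₀ without:

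SE² = [A(1 − A) + (n₁ − 1)(Q₁ − A²) + (n₀ − 1)(Q₂ − A²)] / (n₁n₀), where Q₁ = A/(2 − A) and Q₂ = 2A²/(1 + A).

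At A = 0.85, Q₁ = 0.739, Q₂ = 0.781 and A² = 0.7225. Event rates of 10% to 30% are assumed, and visits are treated as independent.

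| Windows | Increases | SE at AUC 0.85 | Observed AUC needed for lower 95% bound above 0.85 |
|---|---|---|---|
| 340 | 34 to 102 | 0.042 to 0.025 | 0.92 to 0.89 |
| 272 | 27 to 82 | 0.047 to 0.028 | 0.92 to 0.90 |
| 150 | 15 to 45 | 0.064 to 0.038 | 0.94 to 0.91 |

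Each person can contribute two visits, so correlation within person would probably widen these intervals.

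**The case against.** The strongest reply is that the window is observed once an increase is read as a visit-to-visit rise in SSI. In both device arms EMA runs through the 14 days before weeks 6 and 12, and those data precede the score being predicted. This stands. A reader might infer from the schedule that the design has no usable two-week window at all, and the 4 covered cells show otherwise. What is lost is the dating of onset, not the order of EMA and assessment.

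A reader might also infer that two thirds of the pre-visit windows follow the increase. That needs a single onset, uniform in time and persisting to the visit. The Protocol itself expects ideation to vary within a person (Supplement Aim 1). If it is episodic, a rise seen at a visit may be recent. EMA following the increase is therefore possible but not shown.

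Third, 150 windows is not a stated figure. The documents do not say who receives the SSI, and people already in follow-up when it was added could contribute a week 6 to week 12 change. The 340-window case belongs beside it.

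Fourth, the SSI is not the only ideation measure. The C-SSRS at about days 7 and 14 does fall while EMA is running. But it reaches only 30 BD participants in one arm and is not the Aim 2 outcome. The interval form at follow-ups is tied to the visits, and the plan does not use it to date onset. The C-SSRS therefore does not resolve the problem.

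Finally, the Protocol does not say how AUC above 0.85 will be judged. Requiring the lower confidence bound to exceed 0.85, or person-level cross-validation, would be a reasonable choice; its absence is not an error.

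**Conclusion.** The point holds in a limited form. Supplement Aim 2 claims a window before the increase itself, and the design cannot locate that window in any arm, because its outcome dates a rise only to 6 or 12 weeks and no listed EMA item narrows this. What the design does support is a window before the assessment, at weeks 6 and 12 in the two device arms: 340 of 765 planned follow-up visits at N=255, or about 150 under the assumption that only the remaining 112 people receive the SSI. No EMA precedes week 24, and Standard Care has none.

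The one-third figure rests on uniform, persistent onset, and the AUC thresholds rest on assumed event rates of 10% to 30% and independent visits. The dating problem depends on none of these. The documents do not support saying that the window is wholly unobserved, or that a high AUC would necessarily reflect ideation already present; it could do so in part. The matter is worth correcting, but it is confined to a supplementary aim.

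**What to change.** Restate Supplement Aim 2 and its Hypothesis 2 in the Protocol, and add the matching analysis to the SAP:

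- **Outcome:** SSI score higher at week 6 or week 12 than at the previous visit.
- **Predictors:** EMA from the 14 days before that assessment.
- **Analysis set:** CBT2go and EMA-only participants. Week 24 and Standard Care are left out of this aim.
- **Comparison:** keep the comparison of accuracy with baseline suicide risk.
- **Wording:** describe the window as before the assessment, not before the increase.
- **Reporting:** give the number of visits and of increases, and the AUC with a confidence interval that accounts for repeated visits per person. State in advance how the 0.85 target will be judged. If by the lower 95% bound, the observed AUC would need to be about 0.89 to 0.92 with 340 windows, or 0.91 to 0.94 with 150, under the assumed event rates.

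This needs no new visits, instruments or data, so it can be applied although the SAP's cover letter describes the trial as completed. The cost is a narrower claim: the results could speak to ideation found at a scheduled assessment, not to warning before it begins.
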